1. INTRODUCTION

1.1. Indication

The purpose of this study is to assess effect of transcranial direct current stimulation (tDCS) on vibratory and proprioceptive sensation in patients with peripheral neuropathy.

1.2. Background and Rationale

Distal symmetric polyneuropathy (DSP) is a common disease and it can occur in up to 30% of those between ages 70 and 80 years, especially those with diabetes or other diseases that can cause neuropathy[1]. Older individuals even without diabetes or other coexisting disease have increased prevalence of PN that puts them at a significantly increased rate of falling and fall-related injury as compared to similarly aged populations without neuropathy[2-4]. Peripheral nerve dysfunction contributes to age related mobility loss and susceptibility to accidental falls due to several factors including impaired proprioception and muscle weakness[5]. Biomechanical gait analyses have shown that patients with PN walk at slower speeds, with shortened stride lengths and greater base widths, stride times and double support times than age-matched healthy controls[6, 7]. Falls among older adults place a significant cost on the US health care system, resulting in over 662,000 hospitalizations and a total cost of over \$30 billion annually[8]. In a prospective follow up study of 32 patients with peripheral nerve dysfunction, 20 had at least one fall over a period of one year. Fourteen of these patients suffered a fall related injury[9]. Ankle proprioception was reduced in all of the patients with fall. Proprioception is likely to be affected early in the disease process, because it is a complex system that requires integration of sensory input from many receptors

Somatosensory in conjunction with visual and vestibular systems convey information about limb and body movement, force, pressure, tension, and movement in space that is needed for motor control[10]. The somatosensory system is responsible for the neural representation of proprioception. Proprioception is usually defined as the ability of the central sensory processing system to identify the position of the body segments and movements in space based on the sensory signals received from sensory receptors[11]. Mechanoreceptors located in joint capsule, ligaments, menisci, musculotendinous unit, and in the skin are involved in sending the proprioceptive feedback signal to the central somatosensory processing areas. Individuals who are deprived from such signals temporarily or permanently due to damage to the sensory nerves show a significant disturbance in movement planning and execution despite having a fully functional motor pathway. Precise ankle proprioceptive thresholds allow earlier perception of a perturbation that is necessary for stabilization or swing limb positioning to prevent falls. Additionally, Standing balance control relies substantively on ankle proprioception. Disrupting proprioception during standing increases body sway that has become part of routine bedside neurologic examination of gait and balance. It has been estimated that ankle proprioception has between 60-70 % contributions to body sway when deprived from other source of sensory feedback such as visual signal[12-14].

Exploring the neural correlates of maintaining balance during upright stand and walking and role of ankle proprioception has been difficult due to the fact that functional imaging are mostly done

with subjects lying down and immobile. The first brain mapping of ankle proprioception-related neural differences in young and older adults was provided in 2011. In this study, stimulating key proprioceptors (i.e., muscle spindles) in the feet with tendon vibration was done during fMRI. In young and older individuals, muscle spindle related neural activity was identified in brain areas that included primary and secondary sensorimotor cortices, secondary associative areas, and basal ganglia[15]. Another fMRI study focused on finding areas in the brain that their activity during proprioceptive stimulation shows high correlation with performance of the subjects in a complex balance task. Areas that were found to have high correlation were right anterior insula, right inferior frontal gyrus (BA 44/45), orbital frontal cortex (BA 47), and the right basal ganglia (pallidum and putamen)[16]. It has been tried to examine the neural correlates of balance control using mental imagery of standing upright while lying supine in an fMRI scanner. Reported areas of activation from these studies include premotor cortex, pre-SMA, dorsolateral prefrontal areas, precuneus, inferior parietal lobe, insula, and cingulate, among others[17, 18].

Objective quantification of proprioception may improve early detection of proprioceptive loss and help quantify this loss with aging. Present methods of proprioception quantification predominantly involve measurement of kinesthesia (ability to detect movement) and joint position sense (JPS). A common measure of kinesthesia is the threshold for perception of slow passive movement. Determining the error associated with active or passive reproduction of a joint angle assesses JPS. The most common used measures are passive or active matching and minimum detectable change in position. For example, one method that has been used to measure the proprioception at the ankle is to place one foot on a footpad that is tilted using a torque machine with a fixed speed. Subjects are asked to report as soon as they feel any movement in their ankle and the direction of the move. The angle when the patient pushes the button is used as threshold of proprioception. The other way of measuring it has been putting the ankle in a range of angles and use the angle that the subjects can report the direction of movement correctly more than 75% of trials as the threshold. Matching technique is asking the patient to reproduce an angle in the joint, either on the same side or on the other side. All of these measures have their own downsides and studies have tried to validate them with controversial results. Overall, it appears that threshold reporting is more sensitive than matching techniques. Functional measures such as time to sway and times walk have also been used to evaluate the effect of treatments such as physical therapy and balance training[19-21].

Currently there is no cure for most of the cases of PN and management is mostly focused on rehabilitation programs. Dynamic balance training has shown to have a modest effect on functional stability in patients with diabetic neuropathy but there is no accepted guidelines regarding a rehabilitation regimen that improve balance and prevent falls in these patients. There is little evidence that proprioception can be improved by exercise or bracing. Biofeedback strategies have only just started to be investigated in patients with PN and the results have not been convincing. Providing proprioceptive signal has not received much attention in developing prosthetic limbs or brain-compute interface protocols until more recently. Few studies have used BCI protocols to provide a tactile signal to prosthetic hands to improve the grip accuracy, but this has not been implemented for gait or balance[8, 10, 22-24].

Usefulness of tDCS in modulating sensory functions has been reported before. For example, it has been shown that anodal stimulation of S1 can increase somatosensory evoked potential (SEP) while cathodal stimulation will reduce it[28]. It has been shown that performance of healthy subjects as well as patients with multiple sclerosis (MS) in a tactile task can be enhanced by anodal stimulation of S1[29]. It has also been reported that stimulation of M1 cortex with tDCS can increase SEP. Stimulation of motor cortex has also been shown to enhance the thermal and mechanical sensation as tested by quantitative sensory testing[30]. Additionally a dual hemispheric protocol -during which S1 on one side is stimulated and on the other side is inhibited to block the interhemispheric inhibitory pathways- has been tested in healthy individuals and has been shown to improve performance in tactile spatial discrimination tasks[31]. Interestingly, the effects of tDCS on sensation can last for several minutes[32]. Effects of tDCS on gait and balance as well as improving tactile and proprioceptive sensation has been tested mostly in patients with stroke or spinal cord injury[33-37]. There is no experiment to our knowledge that has examined the effect of stimulating motor and sensory cortices on enhancing the proprioceptive signal in patients with PN. Enhancing this signal by stimulating cortical areas, theoretically can enhance the impaired proprioceptive signal from the ankle and potentially improve the balance problems caused by it. tDCS has been used before in patients with PN safely and with various degree of success for treatment of neuropathic pain, but no study has ever reported any measures of proprioception or balance[26].

In the current study, we plan to test the hypothesis that tDCS of somatosensory, motor or prefrontal cortices can enhance the proprioceptive feedback received from the ankle joints or other sensory feedback signals important for controlling balance and gait and improve these measures in patients with PN. We plan to recruit patients with PN and measure the proprioception sense of the ankle using joint position sense as well as functional measures such as timed walk and time to sway to compare in these subjects before the stimulation and after the real and sham stimulation.

2. STUDY OBJECTIVES AND ENDPOINTS

2.1. Objectives

Primary Objective:

To evaluate the effect of tDCS on proprioception, defined as the minimum detectable angle of dorsiflexion or plantar flexion at the ankle.

Secondary Objectives:

1. To evaluate the effect of tDCS on the proprioception threshold of the big toe;
2. To evaluate the effect of tDCS on vibratory sensation threshold;
3. To evaluate the effect of tDCS on time to sway when standing with feet together and eyes closed;
4. To evaluate the effect of tDCS on timed walk test;

2.2. Endpoints

Primary Endpoint

Minimum detectable angle of dorsiflexion and plantar flexion of the ankle.

Secondary Measures and Efficacy Endpoints

1. Time to sway when standing with feet together and eyes closed;
2. Vibratory threshold as measured by Rydel Seiffer graduated tuning fork;
3. Distance walked in a timed walk test;

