3. STUDY DESIGN

This study will be performed in patients with peripheral neuropathy who are walking independently, but have complains of balance problems such as recent falls or difficulty walking and show reduced vibratory and proprioceptive sensation during routine neurologic examination. These patients will be tested for proprioceptive and vibratory threshold at the toes and ankles before, during and after receiving anodal tDCS over sensory and motor cortices, as well as sham stimulation. Patients will be blinded and won't know if they are receiving actual stimulation or sham stimulation. Subjects will be asked to participate in 2 sessions. In one of the sessions, decided randomly, the sham stimulation will be applied and during the other session the real tDCS stimulation will be applied. Similar sets of assessments will be performed before, during and after application of real or sham stimulations.

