6.2. Outcome Assessments

6.2.1. Proprioception Measurement

Both minimum detectable change in joint position and position matching techniques will be used.

For minimum detectable change in joint position of the ankle, subject's foot will be placed on a foot pad with adjustable angle. The starting angle will be parallel to the floor. The angle will be changed by 2 degrees in each step and subject will be asked to report as soon as they feel a movement in their ankle with their eyes closed. Direction of movement will be at both dorsiflexion and plantar flexion.

For the matching position of the ankle, the footpad will be positioned in various angles ranging from 5 degree to 45 degree and will be asked to try to match the ankle on the other side with their eyes closed. The angle on the other foot will be measured and recorded. For the same-

side matching, subjects will be asked to remember than angle and try to reproduce it after the ankle is returned to the neutral position.

For measuring proprioception at the big toe, the experimenter will move the toe with steps of 2 degrees at a time and will ask subject to report any change as soon as felt with their eyes closed.

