8. DATA ANALYSIS/STATISTICAL METHODS

8.1. Sample Size Determination

Based on the review of the literature, a sample size of 15-20 patients often time has been used to investigate the effect of tDCS. We plan to recruit 20 patients in this study.

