8.2. Analysis of Primary and Secondary Endpoints

A repeated measure ANOVA will be used to compare the outcome measures before the stimulation, after the real stimulation and after the Sham stimulation.

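### Does the primary endpoint need a rule for combining dorsiflexion and plantar flexion, and a named ankle?

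*Combined protocol and SAP*

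**What the plan says.** The primary objective in section 2.1 concerns proprioception, "defined as the minimum detectable angle of dorsiflexion or plantar flexion at the ankle". The primary endpoint in section 2.2 is "Minimum detectable angle of dorsiflexion and plantar flexion of the ankle".

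On measurement, section 6.2.1 says that the "subject's foot will be placed on a foot pad with adjustable angle" and that "Direction of movement will be at both dorsiflexion and plantar flexion". It does not say left, right or both. Section 3 speaks of ankles in the plural, and section 5 allows the electrode over either motor cortex.

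The analysis is one sentence in section 8.2: "A repeated measure ANOVA will be used to compare the outcome measures before the stimulation, after the real stimulation and after the Sham stimulation". No significance level, multiplicity rule or direction factor is given there or elsewhere. Section 8.1 sets the size by precedent: "We plan to recruit 20 patients in this study". Section 3 has each patient attend two sessions, one real and one sham, with a similar set of assessments in each.

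**The concern.** Each assessment yields at least two primary values per patient, and the plan does not reduce them to one. Three routes are open: average the directions, model direction as a second within-patient factor, or test each direction separately. They differ in error rate and power. In principle the choice could be made after the data are seen.

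The change from 'or' to 'and' adds to the doubt. Taken literally, 'or' could let either direction carry the claim, and 'and' could require both. The unnamed ankle might double the number of values again. The sole primary endpoint is at stake, in a study whose sample size rests on no power calculation that would show which variable was meant.

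**Working it through.** **No figure in the plan to reproduce.** The 20 patients come from precedent, with no effect size, SD, significance level or power. What follows sizes the gap and does not test a stated number.

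**Inputs.** From the documents: n = 20 (section 8.1), two directions (section 6.2.1), three conditions (section 8.2). Assumed: two-sided 5% per test, normal data with equal variances, correlation r between the directions' paired differences from 0 to 0.9, and a standardised paired difference of 0.66. That last value is simply the effect that gives 80% power for a paired t-test at n = 20.

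**1. Separate tests, either counts.** If independent, the false-positive chance is 1 − 0.95² = 9.75%. Simulated paired t-tests give:

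| r | Either direction significant |
|---|---|
| 0 | 9.8% |
| 0.5 | 9.1% |
| 0.8 | 7.9% |
| 0.9 | 7.1% |

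The three-condition ANOVA gives 9.7% to 7.2% over the same range. If both ankles were also tested separately, four independent tests would give 1 − 0.95⁴ = 18.5%, and about 15.9% to 9.5% for r from 0.5 to 0.9.

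**2. Both must succeed.** The error cannot exceed 5%. With an effect of 0.66 in each direction, power falls from 80% to between 64% (r = 0) and 75% (r = 0.9).

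**3. Average, or direction as a factor.** These are one test. With every patient measured in both directions under all three conditions, the condition sum of squares and the condition-by-patient sum of squares in the two-factor model are each twice those computed from the per-patient means. The factor of 2 cancels, and F on 2 and (20 − 1) × 2 = 38 degrees of freedom is unchanged. Simulated false-positive rates when all three conditions are equal are 4.9% to 5.1%.

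**4. The price of averaging.** If only one direction responds, the standardised effect of the mean is 0.33/√((1 + r)/2). That is 0.467 at r = 0 and 0.339 at r = 0.9, with power 51% and 30%. A Holm correction keeps about 70% in that case. If both directions respond equally, the mean has effect 0.66/√((1 + r)/2), which is 0.93 at r = 0 and 0.68 at r = 0.9. It then does at least as well as a single direction.

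**5. Which route does the text support?** Section 2.2 says 'and', section 6.2.1 says both directions are tested, and section 8.2 names one within-patient ANOVA. Together they point to step 3. Step 1 needs two things that no section states: separate tests, and a claim that rests on either one. On the side tested, section 3 calls for similar assessments in both sessions. That does not name an ankle, but changing ankles between sessions would go against it.

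**The case for a change.** The strongest case for a change is that the omission is a fact, whereas the sensible reading is an inference. Section 8.2 lists only the condition levels, so an ANOVA handles the two directions only if someone decides to average them or add a factor, and nothing fixes that decision before the data are seen. The study declares a primary objective and sets out to test a hypothesis, so it cannot be excused as a pilot. The ankle cannot be inferred from the stimulated side either, because section 5 leaves that side open. And the remedy would cost only a few lines.

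Much of this stands. The plan is brief, and neither a combining rule nor a named ankle appears in it. What does not follow is that the plan is wrong. The inflation in step 1 depends on a decision rule the plan never adopts, and even then it stays below 5 percentage points for two directions. The remedy is not neutral: averaging and Holm each win under a different pattern of response, by 20 to 40 points of power in the one-responder case, and nothing in the documents favours one pattern.

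A limit on the reassurance also stands. The rate of about 5% in step 3 covers only the multiplicity from two directions. If real and sham stimulation both shift results from baseline by an assumed 0.2 paired-difference SD, and tDCS adds nothing to sham, the omnibus test on the averaged value rejects in about 14% to 22% of trials. That concerns which contrast is read from the three-condition ANOVA. It arises however the directions are combined, and a combining rule would not cure it.

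**Conclusion.** No change to the plan follows. The shift between 'or' and 'and' is loose wording, which section 6.2.1 settles by measuring both directions. The missing combining rule is a gap that a trial analyst fills in the ordinary way, by averaging or by a direction factor, and these give an identical test of condition. The tested ankle is a detail of conduct, partly covered by the requirement in section 3 for similar assessments in both sessions. No stated figure or rule is shown to be wrong.

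At worst, under separate tests with either counting, the false-positive chance would be about 7% to 10% against an assumed 5% for one ankle. All the magnitudes rest on assumed values for significance level, effect and correlation, and on continuous normal data, although section 6.2.1 moves the pad in 2-degree steps. The absence of a rule is certain; the size of any consequence is not.

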3. STUDY DESIGN

This study will be performed in patients with peripheral neuropathy who are walking independently, but have complains of balance problems such as recent falls or difficulty walking and show reduced vibratory and proprioceptive sensation during routine neurologic examination. These patients will be tested for proprioceptive and vibratory threshold at the toes and ankles before, during and after receiving anodal tDCS over sensory and motor cortices, as well as sham stimulation. Patients will be blinded and won't know if they are receiving actual stimulation or sham stimulation. Subjects will be asked to participate in 2 sessions. In one of the sessions, decided randomly, the sham stimulation will be applied and during the other session the real tDCS stimulation will be applied. Similar sets of assessments will be performed before, during and after application of real or sham stimulations.

4. SUBJECT SELECTION

This study can fulfill its objectives only if appropriate subjects are enrolled. The following eligibility criteria are designed to select subjects for whom protocol treatment is considered appropriate. All relevant medical and non-medical conditions should be taken into consideration when deciding whether this protocol is suitable for a particular subject.

4.1. Inclusion Criteria

Subject eligibility should be reviewed and documented by an appropriately qualified member of the investigator's study team before subjects are included in the study.

Subjects must meet all of the following inclusion criteria to be eligible for enrollment into the study:

1. Evidence of a personally signed and dated informed consent document indicating that the subject (or a legal representative) has been informed of all pertinent aspects of the study;
2. Subjects who are willing and able to comply with scheduled visits, and study procedures and are able to read and participate in all study assessments;
3. Subjects with axonal predominantly sensory large-fiber distal symmetric polyneuropathy confirmed with EMG/NCS.
4. Subjects who are walking independently without use of cane or walker.
5. Subjects with impaired proprioception and/or vibration at the toes/ankle on routine neurologic examination.
6. Age older than 18 years;

4.2. Exclusion Criteria

Subjects presenting with any of the following will not be included in the study:

1. Subjects with weakness in ankle dorsiflexion or plantar flexion;
2. Subjects with other etiologies for gait and balance disorder such as cerebellar ataxia, history of stroke, spinal canal stenosis, untreated B12 deficiency;
3. Subjects who are not able to walk independently;
4. History of seizure or a family history of epilepsy;
5. Cardiac pacemakers; cochlear implants; implanted medication pump.
6. Metal implants in the head, except for dental fillings or implants.
7. Increased intracranial pressure;

8. Pregnancy;
9. History of head trauma;
10. Subjects who are taking neuroleptic medications.

5. STUDY PROCEDURE

The tDCS portion of the experiment will begin with DC current (maximum of 2 mA) stimulation delivered through surface electrodes (TransQE from IOMED®, surface area: 25 cm²) using a Phoresor® II Auto (Model No. PM850, IOMED®, Salt Lake City, Utah 84120, USA). One electrode will be positioned above the left or right primary motor cortex, the other electrode over the forehead [27].

For sham stimulation the electrodes will be placed in the same way as for real tDCS in the absence of real stimulation, this means stimulation will be increased to a current strength near to perception threshold and will be decreased afterwards and set to 0 mA output for the period of 20 min. With this procedure participants are usually unable to differentiate between tDCS and sham stimulation [38].

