6.3. Safety and Risk Assessments

Weak direct currents can be applied non-invasively, transcranially and painlessly. Such application leads to transient changes in corticomotor excitability that is fully reversible.

There are no known risks of percutaneous, transcranial DC stimulation of the brain, other than mild local discomfort at the electrode sites (much less than TMS for example). In the current published studies on humans [27, 38-42], the following objective safety data were reported:

- No heating of electrodes
- No demonstrable changes in the skin underlying electrode placement after a stimulation period similar to the one proposed in this protocol.
- Mild itching sensation in the absence of pain. Never led to stopping a study in any of the previous reports.
- No change in serum neuron-specific enolase (NSE, marker for neuronal damage) in 5 subjects immediately and 1 hour after exposure to 13 min of 1 mA anodal DC to motor cortex
- No changes in diffusion weighted or contrast-enhanced MRI and in EEG after exposure to tDCS.

Several hundred subjects so far without reporting any side effects apart from a slight itching under the electrode and a short phosphene if the stimulation was switched on or off abruptly. A review paper discussed the safety of tDCS in human. tDCS applications over motor and non-cortical areas in healthy individuals, migraine patients, post-stroke patients, and tinnitus patients ,etc. revealed the most common adverse effect after tDCS was a mild tingling sensation, followed by fatigue, then a light itching sensation under the stimulation electrodes. Not as common, but mentioned, were headache, nausea, and insomnia. The review paper concluded that tDCS is associated with very minor adverse effects in healthy humans and patients with varying neurological disorders[43]. Even higher intensities of current has been used for tDCS safely without complications[44, 45].

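### The sham onset is set by the patient's perception threshold, not by the onset of the real session, so the two sessions may be distinguishable in a crossover with a patient-reported primary outcome

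*Combined protocol and SAP*

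**What the plan says.** Section 3 describes two sessions per patient in random order: "In one of the sessions, decided randomly, the sham stimulation will be applied", and the other session is real. It makes masking of the patient a design feature: "Patients will be blinded and won't know if they are receiving actual stimulation or sham stimulation". Assessments are made before, during and after each session.

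Section 5 describes the real session as "DC current (maximum of 2 mA) stimulation delivered through surface electrodes". That is an upper limit. The current actually delivered, the ramp and the duration are not given. For the sham, electrodes are placed as in the real session, and then "stimulation will be increased to a current strength near to perception threshold and will be decreased afterwards and set to 0 mA output". The zero-output period is 20 min. No sham peak, ramp time or hold time is given. Section 5 then supports the method with one cited statement: "With this procedure participants are usually unable to differentiate between tDCS and sham stimulation [38".

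Section 6.3 reports from a review that "the most common adverse effect after tDCS was a mild tingling sensation", followed by fatigue and light itching. Section 7 lists itching under the electrode as an expected event.

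In section 6.2.1 the footpad angle changes in 2-degree steps and the patient, eyes closed, says when movement is felt. Section 8.2 compares the outcomes before stimulation, after real and after sham by repeated measures ANOVA.

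**The concern.** A sham masks well when its onset feels like the onset of the real session. Here the two onsets are defined by different things: the sham by where the patient begins to feel current, the real session by a current that may reach 2 mA. Nothing in section 5 links them for a given patient, so the sham may produce less scalp sensation than the real session.

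Three features of this trial make such a difference matter. Each patient experiences both sessions and can compare them. Section 11.3 requires that patients be told the possible risks, so they may know which sensations to look for. The primary outcome is a spoken report with no physical check: section 6.2.1 describes no catch trials and no need to name the direction correctly, although section 1.2 describes a threshold method that does require this. A patient who believes the session is real and expects to do better may report a step earlier, and that looks the same as a true improvement. The ANOVA in section 8.2 has no information with which to separate the two.

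**Working it through.** The plan gives no figure for masking, such as a correct-guess rate, so there is none to reproduce. The sample size of 20 in section 8.1 rests on precedent and uses no assumption about masking. The check therefore sets the two descriptions side by side and then illustrates what recognition could do.

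**Real and sham as written**

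| Item | Real session | Sham session |
|---|---|---|
| Peak current | At most 2 mA; delivered value not stated | Close to perception threshold; value not stated |
| Onset procedure | Not stated | Up, then down; times not stated |
| Duration | Not stated | 20 min at 0 mA |
| Electrode placement | Described in section 5 | Same as real |
| Expected sensation | Mild tingling or itching (sections 6.3 and 7); no rate given | Not stated |

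Only electrode placement is explicitly matched. Section 6.3 mentions a stimulation period like the one proposed in the protocol, but no real-session period appears anywhere. Equal length cannot be confirmed.

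**Illustration 1, in degrees.** Input from section 6.2.1: one step is 2 degrees. Assumed: a fraction p of all patients recognise the real session and report exactly one step earlier in it, with no other effect.

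Spurious mean gain = 2 × p degrees.

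- p = 0.25: 2 × 0.25 = 0.5 degrees
- p = 0.50: 2 × 0.50 = 1.0 degree
- p = 0.75: 2 × 0.75 = 1.5 degrees

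Order matters. A patient who has the real session first has no sham to compare it with while those data are recorded. If recognition came only from comparison, and half the patients had real second (assumed; section 3 says only that order is random), a recognition fraction p among those patients would give 2 × p × 0.5 = p degrees: 0.25, 0.5 and 0.75 degrees at the same three values. Patients who have sham second could instead recognise the sham and report later in it. That would add to the difference but is not modelled here.

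**Illustration 2, false-positive rate.** Assumed: no true effect, 20 patients, a paired t-test of real against sham at two-sided 0.05 as a simplification of the ANOVA, a share q of patients who recognise the real session, and a shift of b standard deviations (SD) of the paired difference in those patients. The mean shift is q × b and the noncentrality is q × b × √20, with 19 degrees of freedom. Extra variance from mixing the two kinds of patient is ignored.

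| q | b | q × b | Noncentrality | False-positive rate |
|---|---|---|---|---|
| 0.25 | 0.2 | 0.05 | 0.22 | 0.055 |
| 0.5 | 0.2 | 0.10 | 0.45 | 0.071 |
| 0.5 | 0.5 | 0.25 | 1.12 | 0.186 |
| 1 | 0.2 | 0.20 | 0.89 | 0.136 |
| 1 | 0.5 | 0.50 | 2.24 | 0.565 |

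The rate runs from almost nominal to more than ten times nominal, depending entirely on q and b. The documents give neither.

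**The case against.** A reader might infer that the sham fails: that patients will feel one session clearly and the other hardly at all, and so will know which was real. The documents do not support that.

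- Section 5 says that patients usually cannot tell, and cites a paper for it. The source cannot be checked here, so it cannot be said to fail for this sham or for two sessions.
- Close to threshold does not mean below it. The sham may be felt.
- Section 6.3 ranks tingling first among adverse effects and calls it mild. It gives a rank, not a frequency.
- The 2 mA is a ceiling. The contrast with the sham may be smaller than that figure suggests.

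A reader might also infer that assessments made while current is flowing carry the bias into the result. The comparison in section 8.2 uses measurements after stimulation; those made during it are not named. What would matter for the planned analysis is a belief that persists after the session. Nor is it certain that bias would favour tDCS, since that assumes patients expect benefit and act on it.

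All of this stands against a claim of demonstrated unblinding. It does not answer the narrower point. One general statement, qualified by the word usually, does not specify this trial's sham or match it to this trial's real session. The ambiguity about what the sham feels like is itself a reason to define it.

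**Conclusion.** The point holds as a credible and avoidable risk, not as a demonstrated failure of masking. Section 5 defines the sham onset independently of the real onset and gives a duration for the sham only. With both sessions given to every patient, some sensation expected from real stimulation, and a primary outcome that is the patient's own report, the sessions may be distinguishable and expectation could bias real versus sham.

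The size is unknown. The 0.5 to 1.5 degrees and the false-positive rates of 0.055 to 0.565 are illustrations under assumed recognition and assumed shifts, and should not be read as estimates. The point is worth settling before enrolment because the planned analysis cannot correct for it afterwards.

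**What to change.** In section 5, reconcile the sham and real descriptions so that the sham reproduces the onset procedure of that patient's real session before the output is set to 0 mA, and so that total electrode time is the same in both sessions. State the real session's duration beside the sham's 20 min. The investigator sets the actual current and ramp values; nothing here asks for a change to the real stimulation.

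The cost is a wording change in section 5 and in the operator instructions, with the same device and the same two visits. The downside is brief active current in the sham session. The investigator should weigh this when setting the values.
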